4.1.1 Sample Size Re-Estimation

At the time of interim analysis, if the study is not stopped early for effectiveness, then sample size reestimation (SSRE) will be performed to calculate the final analysis sample size. The SSRE will be calculated the same way as was performed prior to the trial with the addition of a propensity score matching rate. This rate will account for the percentage of subjects that were in the Tango Belt treatment group but were not able to match adequately with any subjects in the historical control

group. The annual fall-with-major-hip-injury rate will be updated using data from the 134 subjects in the Tango Belt treatment group as well.

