To estimate performance of the Tango Belt, data on file from real-world use of the Tango Belt in the nursing home setting found airbag deployment in 6 of 6 total serious hip-impacting falls, resulting in no major hip injuries. Therefore, we are 95% confident that the Tango Belt will protect 66% of falls. However, it is possible that the Tango Belt may prove to be even more effective with a larger sample size. Therefore, a group sequential design (GSD) will be utilized. The GSD will include a planned interim analysis at a sample size to detect an 80% protective effect of the Tango belt at 80% power at a planned interim analysis. If a significant difference is found between the prospective Tango Belt subjects and historical controls at the interim analysis, the study will be completed early. If not, enrollment will continue until a final sample size is reached to detect a 60% protective effect of the Tango belt at 80% power and a 5% total level of significance. Exact sample sizes for the interim and final analysis will be calculated once the number of historical control subjects and the rate of falls with major hip injury in the control group are determined. The PASS GSD module will be used to simulate the sample sizes and power using the Pocock alpha-spending function. The steps to calculate the sample size will include:

- 1. Test the historical control time periods to determine if all the time periods can be used, depending on if any time periods differ in fall rate
- 2. From the remaining historical control data, find the fall rate and the total sample size available for the historical control group
- 3. Find the sample sizes for the historical controls and the prospective Tango Belt arm at the interim analysis.
- 4. Find the sample size for the prospective Tango Belt arm at the final analysis; the total sample of historical controls will be used at this look.

To demonstrate these calculations, we assumed subjects were followed for an average of 6 months, an annual fall-with-major-hip-injury rate of 8%, and sufficient historical control subjects to allow 1:4 allocation of subjects to treatment and control. This would require 176 subjects in the prospective Tango belt group and 704 subjects in the historical control group at the interim analysis. At the end of the study (should the

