higher efficacy target not be achieved at interim analysis), 417 total subjects would be required in the prospective Tango belt group and 1688 subjects would be in the historical control group.

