4 SAMPLE SIZE

It is estimated that the sample size will include up to 268 subjects in the intervention group and up to 536 subjects in the historical control group. This estimated sample size includes the minimum sample size required to assess the primary endpoint with an additional 30% increase to account for possible subject attrition.

The sample size for the primary hypothesis will be calculated with 80% power. The annual rate of falls with major hip injury has been estimated between 6% and 10% in higher-risk populations within long-term care facilities. Since the fall rate is not exactly known in the study population, the fall rate observed in the historical control group, a nuisance parameter, will be used for sample size calculations. After roughly 70% of subjects were enrolled into the historical control group, the proportion of subjects who experienced a major hip injury due to a fall was calculated to be 15% and this rate was used in the sample size calculation.

The following steps were used to calculate the sample size (for further details, see section 10.1 of the Protocol):

1. Test the historical control time periods to determine if all the time periods can be used, depending on if any time periods differ in fall rate

- 2. From the remaining historical control data, the fall rate was calculated and the total sample size available for the historical control group
- 3. The sample sizes for the historical controls and the prospective Tango Belt arm at the interim analysis was calculated.
- 4. The sample size for the prospective Tango Belt arm at the final analysis was calculated using the total sample of historical controls.

This sample size determination was made based on the following specifications:

Primary Effectiveness Endpoint Assumptions:

The following assumptions were made for estimating sample size for the primary effectiveness endpoint:

- 1. Alpha of 0.025 (one-sided)
- 2. 80% power
- 3. Groups are independent

Based on the above assumptions, the minimum sample required for the intervention group for evaluation of effectiveness (unadjusted) is 94 subjects. At least 134 subjects will be enrolled to the intervention group to account for subject attrition and missing data (estimated to be 30%).

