7.2 PRIMARY EFFECTIVENESS ANALYSIS

The primary effectiveness endpoint for this study is the proportion of subjects experiencing major hip injuries due to falls, as reported at the 180-day visit and will be presented for the Tango Belt and control groups using the ITT and adherence populations.

The proportion of subjects experiencing major hip injury due to falls is defined as the total number of subjects who experience a major hip injury due to a fall divided by the total number of subjects.

The primary effectiveness hypotheses are:

$$\begin{array}{l} H_0 \colon \pi_T \ \geq \ \pi_C \\ H_1 \colon \pi_T \ < \pi_C \end{array}$$

where π_T and π_C are the proportion of subjects experiencing major hip injuries due to falls in the Tango Belt and control group, respectively.

The null hypothesis (H_0) for this endpoint states that the true proportion of subjects using Tango Belt and experiencing major hip injuries due to falls is greater than or equal to the true proportion of subjects in the control group who experience major hip injuries due to falls. The alternative hypothesis (H_1) states that the true proportion of subjects using Tango Belt and experiencing major hip injuries due to falls is less than the true proportion of subjects in the control group who experience major hip injuries due to falls.

The proportion of major hip injuries by treatment group will be presented along with a 95% confidence interval using the Clopper-Pearson method. H_0 will be tested at a one-sided 0.025 level of significance using a logistic regression analysis to compare treatment groups while controlling for propensity score.

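### SAP 4.1.1 sets the final size by the pre-trial method, but the one documented pre-trial calculation does not give 80% power with the planned logistic test at one-sided 0.025

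*Combined protocol and SAP*

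**What the plan says.** Protocol 10.1 describes a two-look group sequential design. The first look is sized for 80% power against an 80% effect. If that look is not significant, the target for the final size is this: "60% protective effect of the Tango belt at 80% power and a 5% total level of significance". The method is described in one sentence: "The PASS GSD module will be used to simulate the sample sizes and power using the Pocock alpha-spending function". The section names no test statistic and does not say whether the 5% is one-sided or two-sided.

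Its worked example assumes 8% per year, 6 months of follow-up and 1:4 allocation. For the interim: "This would require 176 subjects in the prospective Tango belt group and 704 subjects". The corresponding figures for the end are: "417 total subjects would be required in the prospective Tango belt group and 1688 subjects".

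The SAP later replaces these sizes with 94/188 and 188/376 before attrition, using 15% and 1:2 allocation. SAP 4, 6.5 and 7.2 set one-sided 0.025. SAP 7.2 tests the primary hypothesis "using a logistic regression analysis to compare treatment groups while controlling for propensity score", without saying whether the Wald or the likelihood-ratio statistic is meant. SAP 4.1.1 then sends the final sizing back to the pre-trial method: "The SSRE will be calculated the same way as was performed prior to the trial". It adds only a matching rate and an updated event rate.

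**The concern.** The re-estimation decides how many belt subjects are enrolled in the second stage. No section ties it to the test that will be run. With very few events in the belt group, the choice of statistic changes power a great deal, so a size that gives 80% under one test can fall well short under another. If the instruction to repeat the earlier calculation is followed literally, the trial may claim 80% power for a 60% effect and deliver clearly less.

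**Working it through.** **Inputs.** Control proportion over 6 months: 8% × 0.5 = 4% (protocol 10.1). Belt group: 4% × (1 − 0.80) = 0.8% for the 80% effect, and 4% × (1 − 0.60) = 1.6% for the 60% effect. Alpha: one-sided 0.025 (SAP 4).

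**Boundaries.** Pocock-type spending is α(t) = α·ln(1 + (e − 1)t), with t = 176/417 = 0.422. The first look gets 0.025 × ln(1 + 1.718 × 0.422) = 0.0136, so c1 = 2.208. Spending the rest at the second look gives c2 = 2.174.

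**Step 1: reproduce the protocol sizes.** The unpooled statistic is Z = (pC − pT) / √[pC(1 − pC)/nC + pT(1 − pT)/nT].
- Interim: the standard error is √(0.04 × 0.96/704 + 0.008 × 0.992/176) = 0.00998, so the expected Z is 0.032/0.00998 = 3.21. The normal approximation gives Φ(3.21 − 2.208) = 84%; exact binomial enumeration gives 80.0%.
- Final: the standard error is √(0.04 × 0.96/1688 + 0.016 × 0.984/417) = 0.00778, so the expected Z is 0.024/0.00778 = 3.09. The normal approximation gives Φ(3.09 − 2.174) = 82% at that look; two-look simulation gives 81.5% overall.

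**Step 2: the same sizes under other tests.** Interim power is from exact enumeration or simulation; overall power is from two-look binomial simulation, with rejection at either look counted.

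| Test | Interim, 80% effect | Overall, 60% effect |
|---|---|---|
| Unpooled Z | 80.0% | 81.5% |
| Unpooled Z, continuity-corrected | 71.9% | 76.5% |
| Logistic, likelihood ratio | 65.7% | 72.0% |
| Pooled Z | 48.4% | 64.6% |
| Fisher exact | 44.8% | 62.4% |
| Logistic, Wald | 2.8% | 59.0% |

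The Wald interim figure looks extreme but is easily explained. The belt group expects 176 × 0.008 = 1.4 events and the control group 704 × 0.04 = 28.2. With no belt events (probability 0.992^176 = 24%) the Wald test cannot reject. With one belt event and 28.2 control events the log odds ratio is 1.99 and its standard error √(1/1 + 1/175 + 1/28.2 + 1/675.8) = 1.02. That gives z = 1.95, still below 2.208.

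A small simulation (300 runs) that adds a prognostically neutral propensity covariate to the logistic model changes little. Wald gives 2.7% at the interim and 60% at the final look; likelihood ratio gives 66% and 70%.

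**Step 3: do the SAP's own sizes identify the test?** Interim power for 94/188 at one-sided 0.025 (c1 = 2.157, c2 = 2.201, t = 0.5):
- Taking 15% per year, so 7.5% over 6 months: unpooled Z 71%, likelihood ratio 60%, Wald 9%.
- Taking 15% as the 6-month proportion: unpooled Z 94%, Wald 80%. Wald then gives 86% overall at 188/376.

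Unpooled Z fits neither reading. Wald fits the interim on the second reading but overshoots at the final, so the SAP sizes do not settle which test was used.

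**Step 4: what follows if unpooled Z were used at the re-estimation.** Interim at 94/188, 60% effect, 1:2 allocation, completers, boundaries recalculated for each final size:

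| Control rate over 6 months | Size by unpooled Z | Overall power, Wald / likelihood ratio | Size for 80%, Wald | Size for 80%, likelihood ratio |
|---|---|---|---|---|
| 15% | 135/270 | about 70% / 76% | 165/330 | 150/300 |
| 10% | 210/420 | about 70% / 76% | 260/520 | 230/460 |
| 7.5% | 280/560 | about 70% / 76% | 340/680 | 310/620 |

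The shortfall in size is about 10–11% for the likelihood ratio (for example 150/135 = 1.11) and 21–24% for Wald (for example 260/210 = 1.24).

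**The case against.** The strongest reply is that the documents never name unpooled Z and that the protocol sizes are an illustration the SAP has replaced. Both statements are correct. The match in Step 1 also depends on alpha. Protocol 10.1 leaves the side of its 5% open; at one-sided 0.05 the same sizes give 77% and 82% with the likelihood ratio, and 80% and 84% with an arcsine test. The SAP's 94/188, the most recent sizing on paper, does not fit unpooled Z under either reading of 15%. The phrase about the pre-trial method might also be meant loosely, to cover the SAP's mid-trial calculation.

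A reader might infer that SAP 4.1.1 demonstrably carries an unpooled Z test into the enrolment decision. The documents do not support that, so the Step 4 figures stay conditional, including the possibility of a final size below 188/376.

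A reader might also infer a type I error problem, because unpooled Z is anti-conservative at these counts (about 5.7% overall against 2.5%). That does not follow either: no document proposes unpooled Z for the analysis, and SAP 7.2 specifies logistic regression.

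One thing survives all of this. SAP 4.1.1 tells the analyst to repeat a calculation whose only documented output before the trial misses its stated power under the planned test at the SAP's level. Reading the phrase as the mid-trial calculation does not help, since that one names no test either.

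**Conclusion.** The concern holds in this form. At one-sided 0.025 the protocol 10.1 sizes give about 66% (likelihood ratio) or 3% (Wald) interim power for the 80% effect, and about 72% or 59% overall power for the 60% effect. The stated figure is 80% at each look. A re-estimation done in the same way is therefore not shown to give 80% with the SAP 7.2 test.

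This rests on four assumptions: the 6-month control proportion is 4%; the pre-trial method means protocol 10.1; matching is ignored, and propensity adjustment is left out apart from the neutral-covariate check; and the SAP's alpha applies. The size of any shortfall in the actual re-estimation cannot be fixed from the documents. If unpooled Z were used, it would be about 10 percentage points of power for Wald or 4 for the likelihood ratio. The point should be settled before the re-estimation is run.

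**What to change.** In SAP 4.1.1, remove the reference back to the pre-trial calculation. State instead that the final size is found by simulating the SAP 7.2 test itself, with these elements fixed in advance: the logistic statistic (Wald or likelihood ratio, named), the planned matching ratio, the Pocock level at each look, one-sided 0.025 in total, and the control event rate given as a 6-month proportion. Report the power the simulation gives. If enrolment is capped, state the lower power instead of 80%. In protocol 10.1, mark 176/704 and 417/1688 as a superseded illustration that carries no power claim.

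The work is one SAP sentence, a short note in the protocol and a short simulation. The downside is a less favourable stated power, or a re-estimated size somewhat larger than a more optimistic test would suggest.

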10.1 Statistical Sample Size Determination and Analytical Plans

Historical control data will be utilized from data available in the medical record. Specifically, the rate of falls with major injury will be obtained and analyzed in 6-month retrospective periods from Investigational sites participating in the prospective enrollment of treatment subjects, beginning with the IRB approval date and extending back to 2018. Due to the COVID-19 pandemic restrictions, it is possible that some subjects at participating Investigational sites did not receive the SOC during this time

period. Therefore, if there is any evidence that the rate of falls resulting in major injuries is different for any portion of the 2018–present time frame, historical control data will not be utilized from the time frames with a different fall rate. The sample size for the control group, and therefore the allocation ratio, will be determined by the number of historical controls for which data is available during the selected time periods. It is anticipated that control data will be available to allow 2, 3, or 4 controls for each treatment subject. The annual rate of falls with major hip injury has been estimated between 6% and 10% in higher-risk populations within long-term care facilities. Since the fall rate is not exactly known in the study population, the fall rate observed in the historical control group, a nuisance parameter, will be used for sample size calculations.

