4.1 INTERIM ANALYSES

The study will incorporate a group sequential design (GSD) in which an interim analysis will be performed to detect an 80% protective effect of the Tango Belt at 80% power. If a significant difference is found between the prospective Tango Belt subjects and historical controls at the interim analysis, the study will be stopped, and the Tango Belt deemed superior to SOC alone. If not, sample size reestimation will be completed, and enrollment will continue until a final sample size is reached to detect a 60% protective effect of the Tango Belt at 80% power and a 5% total level of significance.

Following the steps from section 4, we assumed subjects were followed for an average of 6 months, an annual fall-with-major-hip-injury rate of 15%, and sufficient historical control subjects to allow 1:2 allocation of subjects to treatment and control. This would require 134 subjects in the prospective Tango Belt group and 268 subjects in the historical control group at the interim analysis using the Pocock alpha-spending function as well as accounting for 30% attrition. At the end of the study (should the higher effectiveness target not be achieved at interim analysis), 268 total subjects would be required in the prospective Tango Belt group and 536 subjects would be in the historical control group.

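### SAP 4.1.1 re-estimates the sample size with an injury rate that includes belt-arm data, although Protocol 10.1 and SAP 4 take that rate from the historical controls

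*Combined protocol and SAP*

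**What the plan says.** - **Protocol 10.1** treats the control rate as the unknown in the sizing: "the fall rate observed in the historical control group, a nuisance parameter, will be used for sample size calculations". SAP 4 repeats the sentence. Protocol 10.1 sets the interim and final sizes once the number of controls and their rate are known. It describes no re-estimation at the interim.
- **SAP 4** says where the current figure came from. After about 70% of the historical controls had been entered, "the proportion of subjects who experienced a major hip injury due to a fall was calculated to be 15" per cent. SAP 9 also calls it a historical control rate.
- **SAP 4.1** fixes the final target in advance: "enrollment will continue until a final sample size is reached to detect a 60% protective effect of the Tango Belt at 80% power".
- **SAP 4.1.1** applies only if the trial does not stop at the interim. The calculation is to be repeated as before, with a propensity-score matching rate added. The last sentence then says that the annual injury rate "will be updated using data from the 134 subjects in the Tango Belt treatment group as well". It gives no weights, no pooling rule and no step that turns the result back into a control rate.
- **SAP 9**, the list of changes from the protocol, has two sample-size entries: attrition from 20% to 30%, and the control rate from 8% to 15%. Neither the re-estimation nor the use of belt data is listed.

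**The concern.** The sizing formula needs the injury risk without the belt, to which the 60% target reduction is applied. Injuries in belt wearers already reflect whatever protection the belt gives. If they are mixed into the control rate and 60% is then taken off again, part of the effect is counted twice. The input also stops being a nuisance parameter, because it now depends on the observed treatment difference: the better the belt looks, short of crossing the interim boundary, the larger the trial demanded. At stake are the number of frail residents enrolled and whether the final size is pre-specified at all, since one sentence allows several different answers.

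**Working it through.** **Inputs.** "Alpha of 0.025 (one-sided") and "The sample size for the primary hypothesis will be calculated with 80% power" (SAP 4). The interim target is 80% and the final target 60%; allocation is 1:2, with Pocock spending and 30% attrition (SAP 4.1). The rate is 15%. An information fraction of 0.5 at the interim is inferred from 94 of 188 evaluable belt subjects (SAP 2).

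**Boundaries.** Alpha spent at the interim is 0.025 × ln(1 + (e − 1) × 0.5) = 0.0155, so c = 2.157. The final boundary is then c = 2.201 (nominal 0.0139).

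**Formula** (belt n, controls 2n, pooled variance, continuity correction), with d = pC − pT and p̄ = (pT + 2pC)/3:

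- n0 = [c√(1.5 p̄(1 − p̄)) + 0.8416 √(pT(1 − pT) + pC(1 − pC)/2)]² / d²
- n = (n0/4) × [1 + √(1 + 3/(n0 d))]²

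**Reproducing the plan.**

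- Interim, 15% v 3%: n0 = 81.5, n = 94 (stated 94).
- Final, 15% v 6%: n0 = 168.3, n = 185 (stated 188, within 2%).
- Attrition: 94/0.7 = 134.3 and 188/0.7 = 268.6 (stated 134 and 268).

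The match requires 15% to be the risk over the six-month follow-up. SAP 4.1 assumes "an annual fall-with-major-hip-injury rate of 15" per cent; halving that to 7.5% over six months gives 198 and 392 instead.

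**Plain reading: pooled rate in the control slot, true control rate 15%, true effect 60% (belt rate 6%).**

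| Rate used | Value | Evaluable belt n | Against 185 | Enrolled (n/0.7) |
|---|---|---|---|---|
| Historical controls only | 15% | 185 | – | 265 |
| Pooled 1:2, (2 × 0.15 + 0.06)/3 | 12.0% | 237 | +28% | 339 |
| Pooled with all 536 controls (1:4), (4 × 0.15 + 0.06)/5 | 13.2% | 213 | +15% | 305 |

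Enrolled figures are before any matching-rate inflation.

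**Conditioning on a missed interim.** Re-estimation happens only then. With 28/188 control events, 5/94 belt events give z = 2.36 and the trial stops; 6/94 give z = 2.07 and it continues. At 6/94 the pooled rate is 34/282 = 12.1% and n = 236 (+28%). In 200,000 simulated interims at 94/188 with a true 60% effect, 47% miss the boundary. Among those the median re-estimated size is 243 with the pooled rate and 203 with the interim control rate (243/203 = 1.20).

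**Alternative reading: pooled rate converted back under the 60% target.** At 1:2, pC = pooled × 3/(2 + 0.4) = pooled × 1.25.

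- True 60% effect: 0.12 × 1.25 = 0.15, n = 185, no excess.
- No effect: 0.15 × 1.25 = 0.1875, n = 144, which is 22% below 185.

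**The case against.** **The formula is not given.** SAP 4.1.1 does not say that the belt data go into the control slot, and the statistician may intend a back-conversion. This stands in part: pooling is an inference, and the percentages depend on it. But no conversion is stated, and repeating the earlier calculation points away from one. Back-conversion also has its own fault, because it undersizes the trial when the belt does little.

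**A larger trial does not harm validity.** On the plain reading the error runs towards more power, and the extra controls come from records. That is fair, but 339 − 265 = 74 additional belt subjects would be enrolled prospectively in a population with 30% assumed attrition.

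**Stronger readings that the documents do not support:**

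- *The excess grows without limit as the belt improves.* At a true 80% effect the pooled rate is 11% and n = 260 (+41%). The matching interim result, about 3/94 against 28/188, has z of about 2.96 and would stop the trial. About 11% of trials with a true 80% effect still miss the interim by chance, so early stopping removes most of these cases but not all.
- *The new size reveals the belt-arm rate.* The matching rate also enters the size. With 28/188 control events, an enrolled size of 343 fits 7 belt events at 95% matching or 13 at 80%. The formula is also unpublished, and under Protocol 8.3 the sponsor already receives belt-arm serious events through the EDC.
- *Type I error is inflated.* Nothing here shows this. Simulating the pooled rule under no effect gave about 0.021 one-sided, below 0.025.

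**Conclusion.** The contradiction is plain in the text: SAP 4.1.1 brings belt data into a rate that Protocol 10.1 and SAP 4 take from the historical controls, and SAP 9 is silent. As written, the rule does not fix the final size. At a true 60% effect the plain reading raises the evaluable belt group by 28% with 1:2 pooling, or by 15% if all 536 controls are pooled. The back-converted reading gives the planned size at that effect and about 144 against 185 if the belt has no effect.

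These sizes rest on a true six-month control risk of 15%, the pooling weights shown, an information fraction of 0.5, and a sizing method inferred from its match to the SAP's figures. They apply only when the interim is not significant. The point concerns the correctness and pre-specification of the final size. It makes no claim of type I error inflation or of disclosure through the new size.

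**What to change.** Delete the last sentence of SAP 4.1.1. Replace it with a statement that the re-estimation rate is updated from historical-control data only, measured over the same follow-up period as in the sizing calculation, and that the matching rate and attrition are then applied. Naming the period also settles whether 15% is an annual or a six-month figure for this purpose. Add the interim re-estimation to SAP 9 as a change from the protocol, with its justification.

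The cost is a sentence in 4.1.1 and a row in SAP 9. No new data are needed. Compared with the plain reading, the trial would need fewer belt subjects whenever the belt has some effect but the interim is missed.
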